9.5.1.6 Asthma Exacerbations

The following asthma exacerbation-related parameters over the 52 weeks will be summarized by treatment (asthma exacerbation is defined in [Section 6.4.5](#)). The analysis will be performed by exacerbation category wherever specified. The exacerbation categories are: All (mild, moderate; severe); and the combination of moderate or severe, and severe.

- Time to first asthma exacerbation by exacerbation category
- Time to first hospitalization for asthma exacerbation
- The annual rate of asthma exacerbations by exacerbation category
- Duration of asthma exacerbations in days by exacerbation category
- The percentage of patients with at least one asthma exacerbation by exacerbation category
- Time to permanent study drug discontinuation due to asthma exacerbation
- The percentage of patients who permanently discontinued study drug due to asthma exacerbation
- Total amounts (in doses) of systemic corticosteroids used to treat asthma exacerbations

Time-to-event variables will be analyzed using a Cox regression model stratified by age (12 to 17 or ≥ 18). The model will include treatment, region and history of asthma exacerbation in the 12 months prior to screening (Yes, No) as fixed-effect factors, and FEV₁ prior to inhalation and FEV₁ 15 to 30 min post inhalation of salbutamol/albuterol (components of SABA reversibility) as covariates. The estimated adjusted hazard ratio for QMF149 over MF will be displayed along with the associated two-sided 95% confidence interval and corresponding p-value.

Kaplan-Meier analysis stratified by treatment group will be also presented and displayed graphically.

Number of the asthma exacerbation will be analyzed using a generalized linear model assuming the negative binomial distribution including treatment, age (12 to 17 or ≥ 18), and region and history of asthma exacerbation in the 12 months prior to screening (Yes, No) as fixed-effect factors, and FEV₁ prior to inhalation and FEV₁ 15 to 30 min post inhalation of salbutamol/albuterol (components of SABA reversibility) as covariates. The log exposure in years will be included as an offset variable in the model. The estimated rate ratio along with two-sided 95% interval and corresponding p-value will be provided.

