2.3.2 Demographics and baseline characteristics

Demographics and baseline characteristics will be summarized by treatment group using the RAN set. Summaries will include age, gender, race, ethnicity, height, weight, body mass index (BMI), relevant medical history, pre- and post-bronchodilator screening spirometry parameters: (FEV₁ in L and % of predicted FEV₁, FVC, FEV₁/FVC and FEF₂₅₋₇₅), FEV₁ reversibility (in L and %), duration of asthma, history of asthma exacerbations, prior asthma treatment, and smoking history.

Continuous variables will be summarized using descriptive statistics (number of non-missing data, mean, standard deviation, median, first and third quartiles, minimum, and maximum) and categorical variables will be summarized in terms of the number and percentage of patients in each category including a category for missing data if any.

Baseline is defined as the last available measurement before first dose of study drug.

No statistical analyses will be provided for baseline comparability among the treatment groups.

In addition, the following categorizations will be done:

- Age into 12 – 17 years, 18 - 64 years, and ≥ 65 years;
- BMI into ≤ 30.0 kg/m² and > 30.0 kg/m²;
- Duration of asthma into < 1 year, 1 - 5 years, $> 5 - 10$ years, $> 10 - 15$ years, $> 15 - 20$ years, and > 20 years;
- Number of asthma exacerbations in the 12 months prior to the start of the study that required treatment into 0, 1, > 1
- pre-bronchodilator FEV₁ into 50 - $< 60\%$, $60\% - < 85\%$ of predicted FEV₁
- ACQ-7 into < 1.5 , $1.5 - < 2$, $2 - < 2.5$, ≥ 2.5 (< 1.5 will be added in case of protocol deviations)
- prior asthma treatment into ICS medium dose, ICS high dose, ICS/LABA low dose, ICS/LABA other than low dose

Medical history will be coded with the Medical Dictionary for Regulatory Activities terminology (MedDRA) using the most actual version at the time of database lock. History/conditions will be summarized for the RAN set by primary system organ class and preferred term. Verbatim recorded history/conditions will be listed together with the coded terms, date of diagnosis/surgery and whether the problem was ongoing at start of the study.

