2.6.1.3 Multiplicity adjustment

To control the family-wise type-I error rate at the two-sided 5% significance level, a multiple testing procedure based on the trimmed Simes test as described in Brannath et al (2009) will be used. The family for the overall type-I error rate control contains three hypotheses: two hypotheses for the primary endpoint trough FEV₁ and one hypothesis for the key secondary endpoint ACQ-7. Denote the two hypotheses for the primary endpoint as H1 and H2 for comparing QMF149 150/160 µg vs. MF 400 µg and QMF149 150/320 µg vs. MF 800 µg respectively. Similarly, denote the hypothesis as H3 for the key secondary endpoint ACQ-7, for comparing QMF149 vs. MF combined doses.

Below is a brief description of the testing procedure based on the trimmed Simes test in Brannath et al (2009).

Let p₁, p₂, p₃ be the corresponding p-values (2-sided) of the three hypotheses of H1, H2, and H3.

Step 1: Retain both H1 and H2 if p_i ≤ 0.05 **AND** the observed treatment difference for the corresponding p_i is in the wrong direction (i.e. MF is performing better than QMF) for **ANY** i = 1, 2, stop here; otherwise go to Step 2.

Step 2: Reject H1 and H2 if p_i < 0.05 for **BOTH** i=1, 2 and go to Step 3; otherwise go to Step 4.

Step 3: Reject H3 if p₃ < 0.05 and stop;

Step 4: If neither Step 1 nor 2 applies, perform the Bonferroni test to H1 and H2. Thus reject H1 if p₁ < 0.025 or reject H2 if p₂ < 0.025 and stop.

For each of the three hypotheses, the corresponding testing statistics (estimated least square mean difference) follows normal distribution. Hence for H1 and H2, their corresponding testing statistics follow jointly bivariate normal distribution. Therefore this testing procedure controls the overall type I error rate at the 2-sided 0.05 level in the strong sense regardless if the bivariate normal distributions have positive or negative correlations as shown in Brannath et al (2009).

Other than the 3 treatment comparisons mentioned above for the primary and the key secondary endpoint, all other analyses will be performed at the nominal 2-sided 0.05 level (2-sided) without multiplicity adjustment.

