2.6.2.7 Asthma exacerbations

All analyses will base on data as reported on the "Asthma Exacerbation Episodes" eCRF.

In patients with multiple exacerbations, if the start date of an exacerbation was less than 7 days after the end date of a previous episode, then this will be assumed to be one continuous exacerbation with the start date taken from the first episode and the end date from the second or last episode. The worst severity of these episodes will be taken as the severity of the collapsed exacerbation. Collapsing of exacerbation episodes will only be done for efficacy analyses but not for safety analyses of adverse events which includes asthma exacerbations.

Asthma exacerbations starting after the first dose and not later than one day after the date of last dose will be included in the analyses of efficacy.

The following asthma exacerbation-related parameters will be summarized considering the whole 52 weeks of double-blind treatment. The analysis will be performed by exacerbation

category wherever specified. The exacerbation categories are: All (mild, moderate, severe), the combination of moderate or severe, and severe.

The annual rate of asthma exacerbations, by exacerbation category

The (annual) rate of asthma exacerbations will be analyzed using a generalized linear model assuming the negative binomial distribution including treatment, age (12 to 17, ≥ 18 years), region and history of asthma exacerbation in the 12 months prior to screening (Yes, No) as fixed-effect factors, and FEV₁ prior to inhalation and FEV₁ 15 to 30 min post inhalation of salbutamol/albuterol (components of SABA reversibility) as covariates. The log exposure in years will be used as an offset variable in the model (see Section 2.4.1 for the definition of exposure). The estimated rate ratio along with two-sided 95% interval and corresponding p-value will be provided.

Time to first asthma exacerbation, by exacerbation category

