Time-to-event variables will be analyzed using a Cox regression model stratified by age (12 to 17, ≥ 18 years). The model will include treatment, region and history of asthma exacerbation in the 12 months prior to screening (Yes, No) as fixed-effect factors, and FEV₁ prior to inhalation and FEV₁ 15 to 30 min post inhalation of salbutamol/albuterol (components of SABA reversibility) as covariates. For treatment comparisons the estimated adjusted hazard ratio will be displayed along with the associated two-sided 95% confidence interval and corresponding p-value. Kaplan-Meier analysis stratified by treatment group will be also presented and displayed graphically. Patients without an event will be considered as censored at the earliest date of (last treatment + 1, death, last visit). In the interim analysis, patients without an event who are ongoing at the time of interim database freeze will be censored at the DLP. For patients having an event, the start date of the exacerbation will be considered to calculate the time to event (i.e., the number of days from start of treatment up to the event start date).

Time to first hospitalization for asthma exacerbation (only for severe exacerbations possible)

The analysis is similar to time to first asthma exacerbation.

Time to permanent discontinuation of study drug due to asthma exacerbation

The analysis is similar to time to first asthma exacerbation.

Duration of asthma exacerbations in days, by exacerbation category

The duration of asthma exacerbations is defined as the sum of days per patient over all exacerbations and the respective lengths (from start to end date). This will be analyzed for treatment group differences using the van Elteren test stratified for age (12 to 17, or ≥ 18), region and history of asthma exacerbation in the 12 months prior to screening (Yes, No).

Total amounts (in doses) of oral corticosteroids used to treat asthma exacerbations

Total amount (in prednisone-equivalent mg doses) of oral corticosteroid used to treat asthma exacerbations during the 52 week treatment period will be summarized descriptively by treatment group.

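### The exacerbation-rate model adjusts for prior-year exacerbations only as Yes/No although a 0, 1, >1 count is already derived, which costs a little precision in the rate ratio

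*SAP*

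**What the plan says.** SAP 2.6.2.7 analyses the annual rate with a negative binomial model. Besides treatment and age group, the model takes "region and history of asthma exacerbation in the 12 months prior to screening (Yes, No) as fixed-effect factors". The two FEV₁ values from the reversibility test, before and after the bronchodilator, are its only other adjustment terms. SAP 16.1.9.6 repeats the history term as Yes/No. Protocol 9.5.1.6 specifies the same coding: "history of asthma exacerbation in the 12 months prior to screening (Yes, No) as fixed-effect factors".

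The Cox model for time to first exacerbation uses the same factor: "The model will include treatment, region and history of asthma exacerbation in the 12 months prior to screening (Yes, No) as fixed-effect factors". So does the duration analysis, a "van Elteren test stratified for age (12 to 17, or ≥ 18), region and history of asthma exacerbation in the 12 months prior to screening".

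For the baseline table, SAP 2.3.2 categorises "Number of asthma exacerbations in the 12 months prior to the start of the study that required treatment into 0, 1, > 1". Protocol Table 6-1 has exacerbation history recorded at Visit 1 for the clinical database. Neither document puts the count into a model or explains the choice of Yes/No.

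The exacerbation endpoints are secondary. Outside the three confirmatory comparisons, "all other analyses will be performed at the nominal 2-sided 0.05 level (2-sided) without multiplicity adjustment" (SAP 2.6.1.3). SAP 2.10 gives power for trough FEV₁ and ACQ-7 only.

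**The concern.** If patients with several exacerbations in the previous year go on to have more than patients with one, a Yes/No factor pools two groups with different expected rates. In a negative binomial model the unexplained difference is absorbed by the dispersion parameter, which enlarges the standard error of the treatment log rate ratio.

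At stake is the width of the rate-ratio intervals for QMF149 against MF and against salmeterol/fluticasone, in each of the three exacerbation categories. The trial was not sized for these comparisons, so covariate adjustment is one of the few remaining ways to gain precision.

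**Working it through.** **The plan's own power figures.** With 10% dropout there are 360 patients per arm.
- Trough FEV₁: SE = 380 × √(2/360) = 28.3 mL; 100/28.3 − 1.96 = 1.57; power 94.2% per comparison at 0.05 (stated 94%).
- ACQ-7, pooled 720 against 720: SE = 0.80 × √(2/720) = 0.0422; 0.15/0.0422 − 1.96 = 1.60; power 94.5%. Both FEV₁ tests must first succeed: 0.942² = 0.887, and 0.887 × 0.945 = 83.8% if the endpoints are independent. With an assumed correlation of 0.5 between the endpoints it is 85.1% (stated 85%).

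Both figures reproduce, and neither depends on the exacerbation covariate.

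**Inputs for the rate model.** From the plan: 400 per arm. Assumed, because the documents are silent:
- exposure 0.95 years and rate ratio 0.70;
- control rate 0.25 to 1.0 per year and dispersion k 0.5 to 1.5;
- history mix (0/1/>1) from 70/22/8% to 40/35/25%;
- relative rates from 1/1.5/2 to 1/2/4.

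**Formula.** A patient with mean count μ contributes information I = μ/(1 + kμ) on the log rate. A history class with n patients per arm contributes n × I₀I₁/(I₀ + I₁) on the log rate ratio, where 0 is control and 1 is QMF149. SE = 1/√(sum over classes).

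Merging classes 1 and >1 into Yes raises the dispersion there to k′ = (1 + k) × E[μ²]/E[μ]² − 1.

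**Mid-range case.** Rate 0.5 per year, mix 60/25/15%, relative rates 1/1.5/3, k = 1.5. The control means are 0.333, 0.5 and 1.0; the QMF149 means are 0.7 times these.
- Three levels: information 23.33 + 12.73 + 11.05 = 47.11; SE = 0.1457.
- Yes/No: in the Yes class E[μ] = 0.6875 and E[μ²] = 0.53125, so k′ = 2.5 × 0.53125/0.6875² − 1 = 1.81. Information 23.33 + 22.37 = 45.70; SE = 0.1479.
- The SE is 1.5% lower with three levels. Power is Φ(0.3567/SE − 1.96), which gives 67.4% with Yes/No and 68.7% with three levels. The information ratio 47.11/45.70 = 1.031 is worth about 3% more patients.

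**Range over the assumed inputs.**

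| Control rate | Mix % (0/1/>1) | Relative rates | k | SE Yes/No | SE 3 levels | SE reduction | Power |
|---|---|---|---|---|---|---|---|
| 0.25 | 60/25/15 | 1/1.5/2 | 0.5 | 0.1683 | 0.1681 | 0.13% | 56.3% → 56.4% |
| 0.5 | 60/25/15 | 1/1.5/3 | 1.5 | 0.1479 | 0.1457 | 1.5% | 67.4% → 68.7% |
| 1.0 | 40/35/25 | 1/2/4 | 1.5 | 0.1262 | 0.1224 | 3.1% | 80.7% → 83.0% |
| 1.0 | 40/35/25 | 1/2/4 | 0.5 | 0.1006 | 0.0972 | 3.4% | 94.4% → 95.6% |

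Over the whole set the SE falls by 0.1% to 3.4%, and power rises by about 0.1 to 2.3 points. Fitting both codings to simulated trials (200 per scenario) gave SE reductions of 0.1% to 2.9%.

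A further simulation with gradients of 1/2/4 to 1/2/6 (250 runs per scenario) gave 1.2% to 3.9%. Its largest observed power gain, 86% to 90%, is partly simulation noise. At 86% power, z = 1.08 + 1.96 = 3.04, and a 3.9% lower SE gives 3.04/0.961 − 1.96 = 1.20, or about 88.6%.

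**Cox model, same simulated trials.** The SE of the log hazard ratio did not fall; it rose by about 0.1% (for example 0.1367 to 0.1369). The estimate moved slightly away from zero (−0.306 to −0.309), and mean |z| changed by −0.003 to +0.050.

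**Van Elteren strata.** Age 2 × region 6 × history 2 = 24 strata; with three history levels, 36. A pairwise comparison has about 5% of 800 = 40 adolescents. They would be spread over 18 strata instead of 12, about 2 per stratum instead of 3.

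**The case against.** The strongest reply is that the Yes/No factor is a valid prespecified choice, identical in protocol and SAP, and that a gain of this size does not justify an amendment. Its validity is not in dispute; the case rests only on the low cost of the change.

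Four further points carry weight.
- **The count is not a drop-in replacement.** SAP 2.3.2 counts exacerbations that required treatment before the start of the study. The model factor is any history before screening. A patient in class 0 of the count could be Yes in the model. This stands and must be settled in the fix.
- **The magnitude has no anchor in the documents.** No inclusion criterion requires a prior exacerbation, so the share of patients with more than one is unknown. The calculation also omits age, region and FEV₁; any overlap of these with history would shrink the gain. This stands, which is why a range is given.
- **Pooling gains far more.** SAP 2.6.2.7 also averages the two QMF149–MF contrasts. With equal arms and similar variances this cuts the SE by 1 − 1/√2 = 29%. That is true, but it answers the pooled add-on question and does not help the individual doses or the salmeterol/fluticasone comparison.
- **Sparse events favour the simpler factor.** Severe exacerbations alone, hospitalisation, and discontinuation due to exacerbation may be rare. This stands and limits the scope of the fix.

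A reader might also infer that the hazard-ratio intervals are widened, since the Cox model carries the same factor. That does not follow. Adding a prognostic covariate to a Cox model does not shrink the SE of the log hazard ratio, and the simulated Cox fits showed no reduction.

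**Conclusion.** The point holds for the negative binomial rate model only, as an optional refinement. Yes/No coding discards prognostic information that the plan already derives, and inflates the SE of the log rate ratio by roughly 0.1% to 4%. The corresponding power gain is mostly under about 2 points. The size depends on assumed rates, dispersion, history mix and a rate ratio of 0.70; the range describes the scenarios examined and is not a bound.

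A reader might take this as a flaw that undermines the exacerbation results or the trial's main conclusions. The documents do not support that. The adjustment is prespecified and based on pre-treatment history, so it introduces no bias and does not inflate type I error. The analyses are nominal and outside the confirmatory family, and the stated 94% and 85% do not involve this covariate.

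**What to change.** In SAP 2.6.2.7 and 16.1.9.6, replace the Yes/No history factor in the negative binomial model by prior-year exacerbations in three levels (0, 1, >1).
- **Definition.** State one definition (all exacerbations, or only those that required treatment) and one 12-month window (before screening, or before study start), and use it in both the baseline table and the model. Confirm that the database holds the count under the chosen definition; the documents show it only for exacerbations that required treatment.
- **Where Yes/No stays.** Keep it for the van Elteren strata, the trough FEV₁ subgroup analysis and models with sparse events. Name those models, or a rule based on blinded pooled event counts, in advance.
- **Cox model.** Using the three-level factor there is optional and for consistency only.
- **Timing and record.** Settle the change before the interim database freeze, when some sponsor staff are unblinded, and list it in SAP 2.1.5 as a departure from protocol 9.5.1.6.

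The cost is SAP wording, one extra degree of freedom in a trial of about 2000 patients, and two codings of the same history within one endpoint family.

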To estimate the add-on effect of indacaterol (QAB149) to existing MF treatment (in terms of exacerbations), the average difference between QMF149 and MF will be computed for all inferential analyses mentioned above. This difference is interpreted as an average of adding indacaterol to MF, under the assumption that indacaterol effect is not altered by dose of MF. To compute the difference, the QMF149 and MF doses will be pooled by averaging the following contrasts within the specified analyses:

- QMF149 (150/160 µg) vs. MF 400 µg
- QMF149 (150/320 µg) vs. MF 800 µg.

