2.7.1 Serious asthma outcomes

A composite endpoint of serious asthma outcomes is defined as a) asthma-related hospitalization, b) asthma-related intubation, or c) asthma-related death. All serious asthma outcomes and deaths occurring from the time of randomization until the 30 days after permanent discontinuation of study drug will be adjudicated by an independent external committee to determine their asthma relatedness.

The composite endpoint as well as each single component of it will be analyzed for the number of patients with the event. If a sufficient number of events ($\geq 10\%$ of patients) occurs, the composite endpoint and its components will be also analyzed for the time to event and the annual rate of events; similar inferential analyses as described for asthma exacerbations will be performed.

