3. In the next step, results from each copy, obtained from GEE method will be combined for the inference using Rubin's rule. The SAS procedure PROC MIANALYZE will be used for combining the results considering the linear scale and then we will take exponential of combined result to obtain the odds ratio.

The combined effects of QMF149 (150/160 & 150/320 μg) and MF (400 & 800 μg) will be derived by weighting treatment groups equally.

The proportions of patients who achieve a clinically relevant improvement in AQLQ (i.e., decrease of AQLQ score of at least 0.5 from baseline) at the scheduled post-baseline visits (Visit 202, 204, 207, 210, and 214) will be analyzed using the same procedures as mentioned above for ACQ-7, except that baseline ACQ-7 is replaced by baseline AQLQ in all steps.

- **Linear Mixed Model Analysis of Covariance (ANCOVA)**

The following linear mixed ANCOVA model will be used for diary data summarized over 26 or 52 weeks:

Dependent variable = intercept + treatment + age group + region + baseline value + FEV₁ prior to inhalation + FEV₁ 15 to 30 min post inhalation + random effect of center nested within region + error.

Results will be presented with LSM and SE for treatment effects and LSM, SE, associated two-sided 95% confidence interval, and two-sided p-value for all relevant treatment contrasts.

- **Cox regression analysis**

A Cox proportional hazards regression model will be applied in time-to-event analyses to test the null-hypothesis $H_0: \lambda_{\text{QMF}}(t) / \lambda_{\text{Control}}(t) = 1$, where $\lambda(t)$ is the hazard function for the failure time of patients treated with QMF and the control group, respectively. The Cox regression

model will be stratified by age group (12 – 17, ≥ 18 years) and will include terms for treatment, region, history of asthma exacerbation in the 12 months prior to screening (Yes, No), FEV₁ prior to inhalation and FEV₁ within 15 to 30 min post inhalation of salbutamol/albuterol (components of SABA reversibility).

Results will be presented with adjusted hazard ratios for treatment group comparisons and associated 95% confidence intervals and two-sided p-values. P-values will be obtained from the Wald chi-squared statistic testing the null-hypothesis that the parameter estimate for the respective treatment effect is 0 (then the hazard ratio is $\exp(0) = 1$).

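### Time to first hospitalization and time to discontinuation for exacerbation have no rule for an arm without events, where the specified Cox Wald test returns p of about 0.99 whatever the other arm's count

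*SAP*

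**What the plan says.** For time to first exacerbation, SAP 2.6.2.7 states: "Time-to-event variables will be analyzed using a Cox regression model stratified by age". The model has treatment, region, exacerbation history and two FEV1 covariates. On reporting it says: "For treatment comparisons the estimated adjusted hazard ratio will be displayed along with the associated two-sided 95% confidence interval and corresponding p-value". For time to first hospitalization, and again for time to permanent discontinuation of study drug due to exacerbation, it says only: "The analysis is similar to time to first asthma exacerbation".

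SAP 16.1.9.6 fixes the test for the time-to-event analyses: "P-values will be obtained from the Wald chi-squared statistic testing the null-hypothesis that the parameter estimate for the respective treatment effect is 0".

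For the add-on effect of indacaterol, SAP 2.6.2.7 promises that "the average difference between QMF149 and MF will be computed for all inferential analyses mentioned above", by averaging the two dose-level contrasts.

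Elsewhere the SAP does guard against sparse events. Section 2.7.1 models adjudicated serious asthma outcomes, asthma-related hospitalization among them, under a condition that opens "If a sufficient number of events" and is set at 10% of patients or more. Section 2.7.2 requires more than 10% for serious adverse events, events of special interest and adjudicated outcomes. The MMRM (2.6.1.2) and the diary percentages (2.6.2.5, 2.6.2.6) have fallbacks for non-convergence. The Cox models in 2.6.2.7 have neither safeguard.

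Protocol 9.5.1.6 specifies the same Cox model with hazard ratio, interval and p-value, but does not name the test.

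**The concern.** Hospitalizations and discontinuations due to exacerbation may be few. A Cox model has no finite hazard ratio for an arm without events, and the Wald test is the one standard test that then loses all its information. The method would therefore fail in the outcome most favourable to an arm: a hazard ratio printed as practically zero, an interval from zero to infinity, and a p-value near 1 even where the counts differ clearly. The pooled QMF149-MF estimate would be lost with it.

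For discontinuation due to exacerbation, SAP 2.1.5 has removed the logistic regression, so the Cox model is the only inferential comparison left. A replacement test chosen after unblinding would be post hoc.

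**Working it through.** **Inputs.** 400 patients per arm and five arms (SAP 2.10). Cox model and Wald test as above. Two-sided 0.05 without multiplicity adjustment (SAP 2.6.1.3). The documents state no event count, rate or power for these two endpoints, so there is no plan figure to reproduce. Event counts and rates below are assumptions.

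**1. Why the Wald test fails.** Take two arms of 400, no events on treatment, k on control. At each event let p = n_t·e^β / (n_c + n_t·e^β), with n_t and n_c the numbers at risk.

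- The slope of the log partial likelihood is −Σp, negative for every β. The likelihood rises without limit as β → −∞, so no finite maximum exists.
- The information is Σp(1−p), about k·e^β for very negative β. Hence SE ≈ e^(−β/2)/√k, and z = β/SE tends to 0.
- For k = 6, stopping after 15 Newton steps gives β = −16.2 and SE of about 1,350. Then z = −16.2/1,350 = −0.012 and p = 0.99. The printed SE depends on the stopping rule; the conclusion does not.

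**2. Other tests on the same data.** At β = 0 with 0 vs 6, the score is about −6 × 0.5 = −3 and the information about 6 × 0.25 = 1.5. Chi-squared is 9/1.5 = 6, p = 0.014.

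| Events (400 per arm) | Wald p | Score p | Penalised LR p | Fisher p |
|---|---|---|---|---|
| 0 vs 4 | 0.99 | 0.045 | 0.055 | 0.12 |
| 0 vs 6 | 0.99 | 0.014 | 0.013 | 0.031 |
| 0 vs 8 | 0.99 | 0.0045 | 0.003 | 0.0075 |

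For 0 vs 6 the Firth hazard ratio is 0.08, profile 95% interval 0.0006 to 0.65.

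**3. The adjusted five-arm model.** Simulated data (5 × 400) were fitted with age strata, treatment, region, history and two FEV1 covariates. Covariate values were assumed and region was simplified to three levels. With no events on QMF149 150/320 and 4 to 16 on MF 800 µg, the Wald p-value was 0.988 to 0.989 every time. With 1 vs 9 the fit was normal: hazard ratio 0.11 (0.014 to 0.86), Wald p = 0.036. The failure is specific to an arm with no events.

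**4. The averaged contrast.** This is ½(β₁ + β₂), with one term infinite. With 3 and 0 events on QMF149 against 12 and 10 on MF, the fitted average was −8.69, SE 453, p = 0.985. Fisher's test on 3/800 vs 22/800 gives 0.00014.

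**5. How often it would matter.** Take 0 vs 6 or more as a clear difference. With independent Poisson counts of means m₁ and m₂, the chance for a given pair is e^(−m₁)·P(N₂ ≥ 6) + e^(−m₂)·P(N₁ ≥ 6).

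| Expected events | Chance |
|---|---|
| No effect: 1, 2, 3 or 4 in both arms | 0.04%, 0.4%, 0.8%, 0.8% |
| Halved: 1 vs 2, 2 vs 4, 3 vs 6, 4 vs 8 | 0.6%, 2.9%, 2.8%, 1.5% |
| 2 vs 6 | 7.5% |
| 1 vs 4 | 7.9% |

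**The case against.** Little rests on these analyses. They are secondary, unpowered and tested at nominal 0.05 outside the three-hypothesis family. Kaplan-Meier curves (2.6.2.7), percentages in the time-to-event tables (2.1.5) and patient counts for adjudicated outcomes without any threshold (2.7.1) would all show an arm with no events. A statistician would recognise a log hazard ratio of −16 with an SE above 1,000 as not estimable. This stands, and it limits the priority.

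The SAP also says the two analyses are similar to, not identical with, the exacerbation analysis, and its change history moves the SAS code to a separate document. That leaves room for another method, but none is written down, and 16.1.9.6 states the Wald test for time-to-event analyses generally.

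A reader might infer a much larger risk from the chance that some arm has no events. At 1, 2, 3 or 4 expected events in every arm, at least one of the five arms is empty with probability 1 − (1 − e^(−m))⁵ = 90%, 52%, 23% or 9%; for a given pair the figures are 60%, 25%, 10% and 4%. The documents do not support reading these as the chance that a real difference is missed. They give no event rate, the calculation assumes equal rates, and in most such outcomes the other arm has too few events for a better test to help, as 0 vs 4 shows.

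Extending the 10% event minimum would be simpler. It would remove the meaningless output, but also any inference on these endpoints.

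**Conclusion.** The point holds as a gap in the specification. For an arm with no events, the stated Cox model and Wald test give no finite hazard ratio and p of about 0.99 whatever the other arm's count, and the averaged QMF149-MF contrast fails with them. That part is mathematical and needs no assumption about rates.

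The practical size is modest. On the assumed means, a given pair would show 0 against 6 or more with probability under 1% if there is no effect, and about 1% to 8% under a two- to four-fold reduction. One event in the arm is enough for the model to behave. No rate for either endpoint can be taken from the documents, so these figures are illustrative. It would also be too strong to infer that the trial's confirmatory conclusions, or its display of hospitalizations, are at risk: neither depends on this test. Priority is low to moderate.

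**What to change.** In SAP 2.6.2.7 and 16.1.9.6, for time to first hospitalization and time to permanent discontinuation due to exacerbation only:

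- Fit the same adjusted, age-stratified Cox model with Firth's penalised likelihood.
- Report profile penalised-likelihood confidence intervals and penalised likelihood-ratio p-values, not Wald, for each pairwise comparison and for the averaged QMF149-MF contrast. The test must be named: a Wald test on the penalised fit for 0 vs 6 gives p = 0.10, against 0.013 by penalised likelihood ratio.
- If neither arm of a comparison has an event, report counts and Kaplan-Meier curves only for that comparison.

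Leave the time-to-first-exacerbation analyses unchanged. The cost is a few sentences in the SAP and a little more programming, with no new data. The penalised estimate is pulled slightly towards no effect, which is a small price for a usable interval. Protocol 9.5.1.6 names no test, so its wording on hazard ratio, interval and p-value can stand.
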